#### 4.7.1.2. Safety Subgroup Analyses

For [SUB1]-[SUB8], following analysis will be conducted

[SUB\_SAF1] Proportion of participants who have TEAE Nausea

[SUB\_SAF2] Proportion of participants who have TEAE Diarrhoea

[SUB\_SAF3] Summary of Level 1 hypoglycemia: Glucose <70 mg/dL (3.9 mmol/L) and >= 54 mg/dL (3.0 mmol/L)

- Note: The response variable is incidence, not aggregated rate per year. Statistical model is logistic regression.

[SUB\_SAF4] Summary of Level 2 hypoglycemia: Glucose <54 mg/dL (3.0 mmol/L)

- Note: The response variable is incidence, not aggregated rate per year. Statistical model is logistic regression.

[SUB\_SAF5] Change from baseline in pulse rate (bpm)

Model terms and analysis are summarized in the [Table GBGQ.4.2](#).

#### 4.7.1.3. OAM Subgroup Analyses

All Table/Figure analysis (e.g., demographic, treatment compliance, efficacy, safety) will be conducted for the following OAM subgroups unless otherwise specified.

- DPP-4 inhibitors (DPP-4i)  
Note: This is a monotherapy of dulaglutide.
- Sulfonylureas (SU)
- Biguanides (BG)
- Alpha-glucosidase inhibitors (a-GI)
- Thiazolidinedione (TZD)
- Glinides
- Sodium-glucose cotransporter type 2 inhibitors (SGLT-2i)
- Combination therapy (SU, BG, a-GI, TZD, Glinides, or SGLT-2i)

When statistical models are used (e.g., MMRM, ANCOVA, logistic regression) “pre-study OAM class” model term will be excluded.

For example, for SU subgroup, MMRM model of **Analysis of HbA1c (%)** will include following terms:

- treatment, baseline value, visit, the interaction of treatment-by-visit

The statistical models do not include the OAM subgroup-treatment interaction as a model term. Therefore, no interaction will be tested (using p-value).

The subgroup analysis specified in Section [4.7.1.1](#) or Section [4.7.1.2](#) (e.g. Age, Sex) will not be conducted for the OAM subgroups.

If OAM subgroup results are redundant, they will not be created, for example, “Summary of Dose Modification of Oral Anti-Diabetic Medication” and “Summary of OAM Mean Daily Doses (mg/day)”.

For Kaplan-Meier analysis, odds ratio and p-value will not be produced if estimates are unavailable due to small events or sample size, or figure may not be created.

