## **Randomization:**

Approximately 732 participants will be screened to achieve 585 participants randomly assigned in a 2:1 ratio to dulaglutide 1.5 mg group and dulaglutide 0.75 mg group (390 and 195 participants, respectively).

Randomization at Visit 3 will be stratified by pre-study OAM class and HbA1c at Visit 1.

For participants taking DPP-4i prior to randomization, target numbers of participants randomized for 1.5 mg and 0.75 mg are 150 and 75 (total 225 participants).

For participants taking other OAMs, target numbers of participants randomized for 1.5 mg and 0.75 mg are 240 (40 per OAM class) and 120 (20 per OAM class). In total, 360 participants (60 per OAM class) will be randomized for other OAMs.

The stratification factors are as follows.

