##### **4.7.1.1. Efficacy Subgroup Analyses**

Following subgroup will be used:

[SUB1] Baseline HbA1c (%) (2 groups: value < 8.5, 8.5 <= value)

[SUB2] Age subgroup 1 (years) (2 groups: value < 65, 65 <= value)

[SUB3] Age subgroup 2 (years) (3 groups: value < 65, 65 <= value < 75, 75 <= value)

[SUB4] Sex (2 groups: male, female)

[SUB5] Duration of Diabetes (years) (2 groups: value < median, median <= value)

[SUB6] Baseline Body Weight (kg) (2 groups: value < median, median <= value)

[SUB7] Baseline BMI (2 groups: value < 25, 25 <= value)

[SUB8] Monotherapy or OAM combination (2 groups: Monotherapy, SU/BG/a-GI/TZD/Glinides/ SGLT-2i)

Note that the medians are based on ITT population.

For [SUB1]-[SUB8] following analysis will be conducted:

[SUB\_EFF1] Change from baseline in HbA1c (%)

[SUB\_EFF2] Proportion of participants achieving HbA1c target of  $\leq 6.5\%$

[SUB\_EFF3] Proportion of participants achieving HbA1c target of  $< 7.0\%$

[SUB\_EFF4] Change from baseline in body weight (kg)

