**Table GBGQ.4.2. Statistical Model Term Summary for the Subgroup Analysis**

	A	B	C	D	E	F	G	H
1		Analysis:	CFB A1c (%)	CFB Weight (kg)	CFB Pulse (bpm)	A1c < 7%, <=6.5%	Nausea, Diarrhoea	Hypo Level 1, Hypo Level 2 (Incidence)
2		Outcome type	Continuous (mult-visits)			Binary (single)	Binary (single)	Binary (single)
3		Model	MMRM			Logistic	Logistic	
4		Basic model (each subgroup)	TMT, BASE, visit, TMT*visit			TMT, BASE	TMT	
5		Basic model (combined subgroup)	TMT, BASE, visit, TMT*visit, SUB, SUB*TMT, SUB*visit, SUB*TMT*visit			TMT, BASE, SUB, SUB*TMT,	TMT, SUB, SUB*TMT,	
6	Subgroup	BASE in the model	A1c (conti.)	Weight (conti.)	Pulse (conti.)	A1c (conti.)	None	
7	SUB1	Term adjust	OAM Delete:BASE	OAM	OAM	OAM Delete:BASE	OAM	
8	SUB2-5	Term adjust	OAM	OAM + A1c(stratum)		OAM	OAM + A1c(stratum)	
9	SUB6/7	Term adjust	OAM	OAM + A1c(stratum) Delete: BASE	OAM + A1c(stratum)	OAM	OAM + A1c(stratum)	
10	SUB8	Term adjust	None	A1c(stratum)		None	A1c(stratum)	

Abbreviation: A1c = hemoglobin A1c; BASE=baseline; CFB = change from baseline; cont. = continuous; Hypo = hypoglycemia; Logistic = logistic regression; MMRM = mixed-effects model for repeated measures; OAM = oral antihyperglycemic medication; SUB = subgroup; TMT = treatment

Two statistical models will be used:

[Model 1] Estimation model for each subgroup (denoted as “each subgroup” in [Table GBGQ.4.2](#)).

[Model 2] Interaction tests model for combined subgroup (denoted as “combined subgroup” in [Table GBGQ.4.2](#)).

Model 1 and Model 2 have different covariates. They are summarized in [Table GBGQ.4.2](#).

Example: [SUB1] [SUB\_EFF3] (A1c <7% analysis) each subgroup model will have

[Model 1] (TMT+BASE) + (OAM -BASE) = TMT +OAM.

[Model 2] (TMT+ BASE+ SUB+SUB\*TMT) + (OAM-BASE) = TMT+SUB+ SUB\*TMT + OAM.

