## 5. Sample Size Determination

Approximately 732 participants will be screened to achieve 585 participants randomly assigned in a 2:1 ratio to dulaglutide 1.5 mg group and dulaglutide 0.75 mg group (390 and 195 participants, respectively). Assuming a drop-out rate of 10%, 528 participants will be evaluable for an estimated total of 352 evaluable participants in the dulaglutide 1.5 mg group and 176 evaluable participants in the dulaglutide 0.75 mg group.

This sample size provides at least 90% power for demonstrating superiority of dulaglutide 1.5 mg to dulaglutide 0.75 mg in the HbA1c change from baseline at Week 26. This assumes a true treatment difference of -0.3% with a common standard deviation (SD) of 1.0% for the change in HbA1c from baseline.

For participants taking DPP-4i prior to randomization, target numbers of participants randomized for 1.5 mg and 0.75 mg are 150 and 75 (total 225 participants).

For participants taking other OAMs, target numbers of participants randomized for 1.5 mg and 0.75 mg are 240 (40 per OAM class) and 120 (20 per OAM class). In total, 360 participants (60 per OAM class) will be randomized for other OAMs.

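### Keeping pre-study OAM class in the continuous-outcome models for the pooled combination-therapy subgroup and for SUB8 would give slightly tighter intervals at almost no cost

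*SAP*

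**What the plan says.** Class is a design factor. SAP 1.2 says: "Randomization at Visit 3 will be stratified by pre-study OAM class and HbA1c at Visit 1". SAP 4.1 (Stratification factors) makes inclusion of both factors the default in the models, unless the SAP specifies otherwise. The primary HbA1c MMRM keeps class (Protocol 9.4.3.1; SAP 4.1, Case 2), and so does the ANCOVA in Case 1.

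SAP 4.7.1.3 then lists the OAM subgroups. Seven are single classes. The eighth is pooled: "Combination therapy (SU, BG, a-GI, TZD, Glinides, or SGLT-2i". For the whole list the SAP says: "When statistical models are used (e.g., MMRM, ANCOVA, logistic regression) “pre-study OAM class” model term will be excluded". Its only worked illustration is a single class: "For example, for SU subgroup, MMRM model of" HbA1c, with treatment, baseline, visit and treatment-by-visit as terms.

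SAP 4.7.1.1 defines SUB8 as monotherapy (former DPP-4i users) against the same six classes pooled. In Table GBGQ.4.2, rows SUB1 to SUB7 add OAM. Row SUB8 adds nothing for the HbA1c outcomes and only the HbA1c stratum for the others. The table has one adjustment cell per outcome, and it serves both Model 1 (estimation within each subgroup) and Model 2 (interaction test).

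On size, SAP 5 says: "In total, 360 participants (60 per OAM class) will be randomized for other OAMs".

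**The concern.** Within a single class the OAM term is constant and has to go. Within the pooled group it takes six values, is estimable with 60 planned participants per class, and was balanced by the randomization. Leaving a balanced stratification factor out of a linear model puts any between-class variance into the residual. The usual model-based standard error then overstates the uncertainty of the treatment difference.

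What is at stake is some precision in the continuous-outcome results for combination therapy (HbA1c, FSG, body weight, SMBG, vital signs, laboratory values) and in the SUB8 interaction test. The group is large, and SAP 4.7.1.3 repeats nearly all tables and figures for it. No decision rule or stated power depends on these results.

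**Working it through.** **The plan's own figure.** SAP 5: "This assumes a true treatment difference of -0.3% with a common standard deviation (SD) of 1.0% for the change in HbA1c from baseline", with 352 and 176 evaluable. SE = 1.0 × sqrt(1/352 + 1/176) = 0.0923; 0.3/0.0923 = 3.25; 3.25 − 1.96 = 1.29, which gives power of 90.1%. The stated figure of at least 90% reproduces.

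**Inputs for the combination group.**
- From the documents: 240:120 randomized, less 10% drop-out, gives 216:108 evaluable, or 36:18 in each of six classes. Baseline range is 8.0 to 10.0%. SD of change is 1.0%.
- Assumed: uniform baseline, baseline slope −0.5, Normal class means with SD τ of 0, 0.1, 0.2 or 0.3% HbA1c, and a single-visit ANCOVA standing in for the MMRM.

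**Formula.** The expected between-class sum of squares is 54 × 5 × τ² = 270τ². Without class, the residual degrees of freedom are 324 − 3 = 321. Hence

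SE ratio (class omitted / class kept) = sqrt(1 + 270τ² / (321 × residual variance)).

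With the SD of change held at 1.0, the residual variance is 1.0 − 0.25 × 4/12 − (5/6)τ² = 0.917 − (5/6)τ².

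| τ | Residual variance | Ratio, formula | Ratio, simulated | SE omitted / kept | Power % for −0.3, omitted / kept |
|---|---|---|---|---|---|
| 0 | 0.917 | 1.000 | 1.000 | 0.1130 / 0.1130 | 76.0 / 76.1 |
| 0.1 | 0.908 | 1.0046 | 1.0046 | 0.1128 / 0.1123 | 75.1 / 75.3 |
| 0.2 | 0.883 | 1.0189 | 1.0187 | 0.1129 / 0.1109 | 75.3 / 76.6 |
| 0.3 | 0.842 | 1.0440 | 1.0435 | 0.1129 / 0.1082 | 76.5 / 79.1 |

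There were 10,000 replicates per row. Coverage without class was 95.1, 94.8, 95.6 and 96.2%, and the bias never exceeded 0.002. With residual SD fixed at 1.0 instead, the excess is 0, 0.4, 1.7 and 3.7%. With residual SD 0.9 it is 0, 0.5, 2.1 and 4.5%.

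**Second route.** If class explains a share R² of the variance left after the other covariates, the width ratio is 1/sqrt(1 − R²). A separate simulation used permuted blocks within class and HbA1c stratum, with 10% random dropout. For R² of 2, 5, 10 and 20% it gave width ratios of 1.009, 1.025, 1.053 and 1.117. The routes agree: τ = 0.3 means R² = 0.075/0.917 = 8.2%, and 1/sqrt(1 − 0.082) = 1.044.

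**SUB8 interaction.** Adding 135:68 evaluable former DPP-4i users gives 527 participants and 527 − 5 = 522 residual degrees of freedom without class. The ratio sqrt(1 + 270τ²/(522 × residual variance)) is 1.000, 1.003, 1.012 and 1.027. Simulated SEs agree: 0.1818/0.1818, 0.1815/0.1810, 0.1805/0.1784 and 0.1789/0.1742.

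**Several visits.** The SAP's MMRM carries class only as a main effect. A three-visit unstructured model (same layout, complete data, correlation 0.5 to 0.7 assumed, 400 replicates) gave 1.8 to 1.9% and 4.2 to 4.4% for τ of 0.2 and 0.3 when class effects were constant over visits. When early effects were one third to one half of the Week 26 effect, the gain fell to 1.2 to 1.7% and 2.8 to 3.8%.

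**Responder models.** At a 47.4% control rate and an assumed conditional log odds ratio of 0.6, the SE without/with class was 0.250/0.252 at class logit SD 0 and 0.250/0.261 at 0.6. Keeping class widens the interval here. At class logit SD 0.6 the estimated log odds ratio was 0.569 without class and 0.617 with it, because the class-conditional odds ratio is a different quantity.

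**The case against.** The case for leaving the text alone has four parts.

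- **No rule is broken.** A reader might infer that 4.7.1.3 contradicts the default in SAP 4.1. It does not: that default yields wherever the SAP specifies otherwise, and here it does.
- **Row SUB8 may be deliberate.** A reader might take the contrast with SUB1 to SUB7 as an oversight. SUB8 is itself a function of OAM class, so an ordinary class main effect would be aliased with SUB in Model 2. That is a sufficient reason for the row to differ, and the documents do not show an oversight. Nesting class within SUB avoids the aliasing and leaves the SUB-by-treatment term estimable.
- **The size is assumed and may be nil.** This stands. The documents give no between-class spread, and the multi-visit check shows that the single-visit figures can overstate the gain.
- **The gain does not extend to logistic models.** This also stands, and it limits the fix. The precision argument covers continuous outcomes only. Cox and negative binomial models were not examined, and SAP 4.1 already reports a convergence problem with the planned hypoglycemia rate model.

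These points keep the matter small. They do not remove it for the continuous models, where keeping class has no SE penalty if class proves irrelevant (ratio 1.000).

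**Conclusion.** An optional efficiency improvement, not an error. For continuous outcomes in the combination group, omitting class inflates the model-based SE by about 0 to 4.4% for class-mean SDs of 0 to 0.3% HbA1c. The power difference is at most 2.6 percentage points (79.1 − 76.5). The SUB8 interaction SE is inflated by at most about 2.7%. All of this rests on the assumed class spread, and on class effects that are roughly constant over visits; otherwise the gain is smaller.

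A reader might go further and infer biased subgroup estimates or an inflated type I error. Neither follows. With arms balanced within class, the estimate is unbiased and the intervals err on the wide side. The simulations assumed that dropout does not disturb that balance. The primary and whole-population analyses keep class and are unaffected.

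**What to change.** For MMRM and ANCOVA models only:

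- **SAP 4.7.1.3:** limit the exclusion of pre-study OAM class to the single-class subgroups, and keep the term for combination therapy.
- **Table GBGQ.4.2, row SUB8, continuous-outcome cells:** state the terms separately. Model 1 monotherapy has no OAM term, Model 1 combination adds OAM class, and Model 2 adds OAM class nested within SUB.

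Make both edits together. The SUB8 Model 1 for HbA1c change in the combination group and the 4.7.1.3 combination-therapy model are now the same model. Changing only one would give two estimates for the same participants.

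Leave the logistic (HbA1c target and safety), Cox and negative binomial subgroup models as written.

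The cost is one sentence, the SUB8 cells for continuous outcomes (which need a departure from the table's one-cell-for-both-models layout) and about five degrees of freedom. No new data are needed.

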## **4.8. Interim Analyses**

The first database lock (DBL) and unblinding will occur, and the interim analysis, including all data up to Week 26. It does not include follow-up period data for safety analysis.

If an AE is continuing at the timing of the interim (week 26), its end day of the AE is temporarily assumed to be Week 26 (Week 26 imputation method). This will minimize the AE duration length estimation bias. If we eliminate these events from the duration analysis, the duration will be shorter than the Week 26 imputation method, which is not ideal. At the final DBL, an actual AE end day will be replaced.

Suppose a patient discontinues the study before Visit 7 (their last visit will be Visit 801) and he does not have Visit 7. Then the interim analysis will include the data captured by the maximum scheduled visit in Study Period 1.

The interim analysis only includes maximum scheduled visit data in Study Period 1. Hence the unscheduled one (e.g., Visit 7.1) will be out of scope.

Visit 801 (early termination visit) may be included in some TFLs, for example, disposition.

The final database lock will then be conducted after all participants have completed the Follow-Up Period.

If an AE is continuing at the timing of the final database lock, its end day of the AE is assumed to be the end of his/her study completion day.

Unblinding details are specified in a separated unblinding plan.

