At Week 52 or the early termination (ET) visit, all used and unused study intervention will be returned.

Discontinuation or dose changes of concomitant OAMs are not permitted, except in certain situations (Section 6.5). Participants will be permitted to use concomitant medications that they require during the study, except certain medications that may interfere with the assessment of efficacy and safety characteristics of the study intervention (Section 6.5).

Safety Follow-Up Period

Procedures during the safety follow-up period will be performed as shown in the SoA (Section 1.3).

All participants who complete the treatment period (both I and II) are required to complete Visit 801, a safety follow-up visit approximately 4 weeks after the last visit of the treatment period. During the safety follow-up period, participants will not receive study intervention.

The safety follow-up period will also be applied to participants who discontinue from the study. In this case, the Safety Follow-Up visit (Visit 801) will occur approximately 4 weeks after the ET visit.

Participants are required to return any remaining study diaries to the study site at the end of this period.

Early Termination Visit

Every attempt will be made to keep participants in the study irrespective of their adherence to treatment with study intervention.

At any time after Visit 3 (randomization), a participant who is to discontinue from the study before Visit 9 will have an ET visit conducted. At this visit, procedures will occur as shown in the SoA (Section 1.3). Participants should be instructed to return any remaining used or unused study intervention supplies and diaries to the study site at this visit. Participants will be asked to perform the Safety Follow-Up visit (Visit 801) approximately 4 weeks after the ET visit, so that the Safety Follow-Up visit (Visit 801) will be their final visit. If the participant is not able to perform the Safety Follow-Up visit (Visit 801), the ET visit will be the final study visit. A participant summary electronic case report form (eCRF) will be completed.

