**Early Termination (ET) Visit:**

Every attempt will be made to keep participants in the study irrespective of their adherence to treatment with study intervention.

At any time after Visit 3 (randomization), a participant who is to discontinue from the study before Visit 9 (Week 52) will have an ET visit conducted. At this visit, procedures will occur as shown in the Schedule of Activities (SoA, Protocol Section 1.3). Participants should be instructed to return any remaining used or unused study intervention supplies and diaries to the study site at this visit. Participants will be asked to perform the Safety Follow-Up visit (Visit 801) approximately 4 weeks after the ET visit, so that the Safety Follow-Up visit (Visit 801) will be their final visit. If the participant is not able to perform the Safety Follow-Up visit (Visit 801), the ET visit will be the final study visit. A participant summary electronic case report form (eCRF) will be completed.

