**Table GBGQ.3.1. Populations and Analysis Sets**

Populations or Analysis Sets	Description
Entered	All participants who sign the ICF.
Randomized	All participants who are randomized to a treatment arm.
Nonrandomized	All participants entered, but not randomized to a treatment arm.
Intention-to-treat (ITT) Population	All randomly assigned participants who are exposed to at least 1 dose of study intervention for an assigned treatment arm. Participants will be included in the treatment group they were randomized to.
Efficacy analysis set for Period I (EAS1)	Data obtained during Treatment Period I (26-week) from the ITT population, excluding data after initiating rescue antihyperglycemic medication or discontinuing study intervention (last dose date + 7 days). In the event of a treatment error, participants will be analyzed according to the treatment they were randomly assigned to receive.
Safety analysis set for Period I (SS1)	Data obtained during Treatment Period I from the ITT population, regardless of adherence to study intervention or initiation of rescue antihyperglycemic medication.
Efficacy analysis set for Period I and II (EAS2)	Data obtained during Treatment Period I and II (52-week) from the ITT population, excluding data after initiating rescue antihyperglycemic medication or discontinuing study intervention (last dose date + 7 days). In the event of a treatment error, participants will be analyzed according to the treatment they were randomly assigned to receive.
Safety analysis set for Period I and II (SS2)	Data obtained during both Treatment Period I, II and safety F/U period from the ITT population, regardless of adherence to study intervention or initiation of rescue antihyperglycemic medication.

Abbreviations: ICF = informed consent form; F/U = follow-up.

Treatment Groups and Comparisons for Each Study Period and Analysis Population are defined as follows.

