For variables that are not collected at each post-baseline visit, data may exist at visits where the variable was not scheduled to be collected. In these situations, data from the early discontinuation visit that do not correspond to the planned collection schedule will be excluded from the MMRM or GLM analysis (Andersen and Millen 2013). Also, for by-visit summaries/displays such as boxplots, the weeks when data was not scheduled to be collected may not be displayed. However, unscheduled assessments within any defined study period will still be used in the shift analyses, and for imputing values for the change from baseline to last observation carried forward (LOCF) endpoint analyses.

If there are no patients in planned TFLs, they may not be created. (e.g., specific AESI TFLs.)

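### SAP 4.8 gives two incompatible scopes for the Week 26 lock and labels Visit 801 as the early termination visit, so late events and ET safety values of early leavers could be left out of SS1

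*SAP*

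**What the plan says.** SAP 4.8 describes the Week 26 lock as "including all data up to Week 26. It does not include follow-up period data for safety analysis". For a participant who leaves the study before Visit 7 and has no Visit 7, it then says: "Then the interim analysis will include the data captured by the maximum scheduled visit in Study Period 1". It goes on: "The interim analysis only includes maximum scheduled visit data in Study Period 1", and places unscheduled visits out of scope, with Visit 7.1 as the example. Finally: "Visit 801 (early termination visit) may be included in some TFLs, for example, disposition".

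Four other places bear on this.

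- SAP Table GBGQ.3.1 defines SS1 as "Data obtained during Treatment Period I from the ITT population, regardless of adherence to study intervention or initiation of rescue antihyperglycemic medication". It has no cut at the last scheduled visit.
- SAP 4.1 says that "unscheduled assessments within any defined study period will still be used in the shift analyses". The same paragraph keeps off-schedule early-discontinuation values out of the MMRM and GLM analyses.
- Protocol 4.1, on participants who discontinue from the study: "In this case, the Safety Follow-Up visit (Visit 801) will occur approximately 4 weeks after the ET visit". SAP 1.2 agrees: "Participants will be asked to perform the Safety Follow-Up visit (Visit 801) approximately 4 weeks after the ET visit".
- The Schedule of Activities (protocol 1.3) gives ET its own column, which includes adverse events, ECG and the safety laboratory panels.

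**The concern.** The two scopes in 4.8 cannot both be programmed. Take a participant last seen at Visit 5 (Week 8) who leaves with an ET visit at Week 13. Under the first scope and the SS1 definition, everything to Week 13 counts. Under the second, if ET is not a scheduled Period I visit, the data stop at Week 8. The event that led to leaving may lie in the five weeks that are cut.

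The Visit 801 label makes this worse. If ET and Visit 801 are treated as one visit, the exclusion of follow-up data and the permissive wording about some outputs could both be applied to ET data.

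The outputs at stake are Week 26 TEAE incidence, AEs leading to discontinuation, treatment-emergent abnormal laboratory results and the calcitonin shift table. Protocol 9.5 assigns the Period I safety analysis on SS1 to this lock. Incidence of TEAEs and discontinuation of study intervention due to AEs, both through 26 weeks, are secondary endpoints. Early leavers are not a random sample, so any loss would be selective.

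There is also a possible mismatch of events and time. The gastrointestinal Kaplan-Meier analysis censors at study discontinuation, and the hypoglycemia rate model uses exposure days as its offset. If events were cut at the last numbered visit but time was not, lost events would become event-free time.

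**Working it through.** **1. The plan's own figures.** Inputs from SAP 5: difference 0.3, SD 1.0, 352 and 176 evaluable, 585 randomized, drop-out 10%. Two-sided alpha 0.05 is from protocol 9.4.1.

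- Standard error = 1.0 × √(1/352 + 1/176) = 0.0923. Power = Φ(0.3/0.0923 − 1.96) = Φ(1.29) = 0.901, which agrees with the stated 90%.
- 585 × 0.9 = 526.5 against 528 stated, and 528/0.9 = 587 against 585 stated. Both agree to within rounding of the plan. These figures are not in dispute; they only size the group.

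**2. Who is exposed.** 585 − 528 = 57 participants: 390 − 352 = 38 (9.7%) on 1.5 mg and 195 − 176 = 19 (9.7%) on 0.75 mg. Under the planned drop-out this is an upper bound on study leavers before Visit 7. A participant can also be non-evaluable through rescue, stopping treatment or a missing value while staying in the study. Those who only stop study drug keep their numbered visits (protocol 7.1).

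**3. How many might have an event at risk.** The documents do not give the share who leave because of an adverse event. Assuming shares of 25%, 50% and 100%, equal in both arms:

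- 57 × 0.25 = 14 participants (2.4% of each arm)
- 57 × 0.50 = 29 participants (4.9%)
- 57 × 1.00 = 57 participants (9.7%)

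These count participants whose event could be affected on the strict reading. They do not count events lost.

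**4. How much time the strict reading removes.** Numbered visits from randomization to the end of Period I fall at Weeks 0, 2, 8, 16 and 26, so the gaps are 2, 6, 8 and 10 weeks, and 10 weeks is the most one participant can lose. If leaving times are uniform over 26 weeks (an assumption), the mean loss is the sum of squared gaps divided by 2 × 26:

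- all visits: (4 + 36 + 64 + 100)/52 = 204/52 = 3.9 weeks
- clinic visits only (gaps 8, 8, 10): (64 + 64 + 100)/52 = 228/52 = 4.4 weeks

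**5. Laboratory and ECG data.** In the Schedule of Activities, hematology, chemistry, lipids, pancreatic enzymes, calcitonin, urine tests and ECG are done at Visits 1, 3, 7, 9, ET and 801. Within Period I after baseline, that leaves Visit 7 and ET. Someone who leaves before Visit 7 therefore has ET alone. If ET is left out, that person contributes no scheduled post-baseline value of these tests to SS1.

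**6. What the exclusion could reach.** SAP 4.1 already keeps off-schedule ET values out of MMRM and GLM on purpose, so those models lose nothing that they were meant to have. The exposed laboratory outputs are the treatment-emergent abnormal results and the shift analysis, where 4.1 keeps off-schedule values and 4.8 appears to remove them.

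**The case against.** The strongest reply is that the SAP nowhere says these data are dropped. ET has its own column in the schedule and is required of anyone leaving before Visit 9, so it can be read as the last scheduled visit of an early leaver. Nothing is then lost. The only excluded visit that 4.8 names, Visit 7.1, comes after Visit 7. Adverse events are collected on their own form up to the follow-up visit, and 4.8 does not say they are cut by onset date. Tables of AEs leading to discontinuation of study drug and of study are planned. SAP 1.2 keeps ET and Visit 801 apart. SS2 at the final lock covers both periods and follow-up without this cut.

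All of this stands, and it rules out treating the loss as certain. It does not settle the text. The SAP never says that ET counts as a scheduled Period I visit. The one sentence in 4.8 that uses the ET name attaches it to Visit 801 and lets it into some outputs only. A programmer following 4.8 literally could leave ET data out. Counting ET as scheduled would also leave the conflict over unscheduled assessments between 4.8 and 4.1.

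**Conclusion.** SAP 4.8 contradicts itself on the scope of the Week 26 lock. It also conflicts with the SS1 definition and with SAP 4.1 on unscheduled values, and it mislabels Visit 801. On a strict reading, Week 26 TEAE incidence, AEs leading to discontinuation, and treatment-emergent abnormal and shift outputs could be understated. At most about 57 of 585 participants are exposed, if the planned drop-out holds.

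A reader might infer that events leading to withdrawal do drop out of SS1, and that harm is therefore understated, more so in the arm with more early leavers. The documents do not support that. The loss depends on ET not counting as a scheduled visit and on AEs being cut by visit, and neither is stated. Leaving rates by arm and the share leaving because of AEs are not given, so the size and direction of any bias between arms are unknown.

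The effect is limited to Week 26 outputs. SS2 should recover the data at the final lock; the SAP does not say whether SS1 is rerun then. The primary HbA1c analysis is unaffected: it is run on EAS1 with measurements at Weeks 8, 16 and 26. The change should be made before the lock, but nothing in the trial's main conclusion depends on it.

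**What to change.** In SAP 4.8, replace the maximum-scheduled-visit rule for SS1 with a rule by date.

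- Include all adverse events and all scheduled, unscheduled and ET assessments from first dose to the date of Visit 7, or to the ET date for participants who leave the study earlier. State a fallback date for anyone with neither visit.
- Exclude only Visit 801 follow-up data and data after Visit 7.
- Name ET and Visit 801 (safety follow-up) separately.
- State that ET and unscheduled values enter the AE, treatment-emergent abnormal and shift outputs, and that off-schedule ET values stay out of MMRM, GLM and by-visit models as in SAP 4.1.
- Apply the same cut to event counts and to the exposure or censoring time paired with them.

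The cost is a few lines of SAP text and the data-cut program. Sites collect nothing new.
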